12.5.2 Multiplicity

The primary variable is only tested for superiority when the non-inferiority is demonstrated by the primary analysis, which will not lead to inflation of the Type-I error.

The statistical analyses on secondary variables are of exploratory nature. No adjustment for multiplicity is needed.

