With 100 subjects per treatment arm superiority of BT524 can also be tested with a power of >80% (t-test, alpha=0.05 2-sided, effect size  $\Delta$ =0.5).

PPD

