6.2 Sample Size Considerations

The non-inferiority margin is defined as 150 mL blood loss, as such difference in blood loss after the decision to treat the subjects with IMP is considered as clinically not relevant.

It is assumed that BT524 is non-inferior that means not worse than FFP/cryoprecipitate with a non-inferiority margin of 150 mL in reducing intra-operative blood loss. Assuming a blood loss of about 500 mL in the FFP/cryoprecipitate treatment arm after the decision to treat the subject with IMP until end of surgery, a standard deviation (SD) of 375 mL, a non-inferiority margin of 150 mL, an alpha-level of 2.5% (1-sided) 100 evaluable subjects per treatment arm are needed to demonstrate the non-inferiority of BT524 by using a t-test (equivalence) with 80% power.

Based on the results of the blinded sample size recalculation (see section 6.2.1) the power was reduced from 90% to 80% to allow an increase of the originally assumed SD of 325 mL to 375 mL.

The sample size will be recalculated at the interim analyses as defined in section 10.0. Sample size estimations will be performed using nQuery Advisor Version 4.0 or higher.

With 100 subjects per treatment arm superiority of BT524 can also be tested with a power of > 80% (t-test, alpha=0.05 2-sided, effect size Δ =0.5).

It is expected that approximately 10% of the randomized subjects will not fulfil the criteria to be included in the PPS. Therefore, approx. 220 randomized subjects are required to reach 200 evaluable subjects in the PPS.

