10.0 Interim Analyses and Data Monitoring

To ensure subject safety, the safety data will be evaluated by a DSMB at regular intervals. A DSMB charter and list of required tables and listings is available (see Appendix 1).

After 40 subjects have completed the study, a blinded sample size recalculation will be performed. See section 6.2.1 for details. A specification of required table and listing is available (see Appendix 1).

In this study, three interim analyses of the observed blood losses are planned to have the option of adjusting the sample size needed.

For this purpose, an alpha-adjustment according to Haybittle/Peto (Haybittle, 1971; Peto et al., 1976; Schulz and Grimes, 2005) is planned. This leads to local alpha levels of 0.001 for each interim analysis and a significance level of 0.05 for the final analysis to reach a global significance level of 5%.

Past interim analyses were based on the PPS, and past sensitivity analyses were based on the mFAS.

The first interim analysis is planned with approximately 50 spine subjects, the second one with at least 40 cytoreductive PMP subjects and all other evaluable spine subjects at that time point. The third interim analysis is planned after approximately 80% of subjects of the total sample size.

Aim of all interim analyses is to adapt the sample size according to the observed blood losses and the SDs:

- a) Early termination due to non-inferiority of BT524 in comparison with the used standard therapies.
- b) Continuation with the sample size as initially planned.
- c) Adjustment of sample size to take into account changes from the previous assumptions on the additional blood loss.
- d) Stopping the study early due to futility if the sample size re-estimation indicates a much higher number than planned before.

As soon as the approximate required number of subjects for an interim analysis has received at least one dose of IMP prior to the end of surgery, completed treatment, the relevant data points (including measurement and documentation of blood loss between decision to treat and end of surgery) have been satisfactorily reviewed and the corresponding items/forms have been frozen, a data snapshot will be taken. Further details are specified in the Planned Data Deliverables section of the Data Management Plan. Classification of PDs as major or minor will be agreed PD review meeting and then reviewed during the BDRM meeting based on the snapshot data.

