12.5.1.1 Assessment of Superiority

If the non-inferiority is demonstrated by the primary analysis, then superiority will be assessed in the FAS and mFAS and repeated for surgery type, sex and race. For superiority analysis, the null hypothesis is that the blood loss in BT524 treatment arm is greater than that in FFP/cryoprecipitate treatment arm. The alternative hypothesis is that the blood loss in BT524 treatment arm is less than that in FFP/cryoprecipitate treatment arm.

H0: $\mu 1 - \mu 2 \ge 0$ H1: $\mu 1 - \mu 2 < 0$ where $\mu 1$ and $\mu 2$ are the same as above.

The same ANOVA model as the non-inferiority analysis will be used. The least square means and difference of least square means will be presented together with the 95% confidence intervals and 2-sided p-value. The superiority of BT524 is demonstrated if the 2-sided p-value is less than 0.05.

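### The SAP's claim that superiority testing adds no Type-I error ignores the interim stops for non-inferiority: on the natural reading the one-sided superiority error is about 4-5%, not 2.5%

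*SAP*

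**What the plan says.** SAP 12.5.2 (Multiplicity) says of the blood-loss endpoint: "only tested for superiority when the non-inferiority is demonstrated by the primary analysis, which will not lead to inflation of the Type-I error". It does not mention the interims.

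SAP 10.0 and Protocol 10.8 plan three interims at local alpha 0.001 each, with 0.05 at the final analysis. Option a), listed for all of them, is "Early termination due to non-inferiority of BT524 in comparison with the used standard therapies". On timing, "The first interim analysis is planned with approximately 50 spine subjects"; the second needs at least 40 PMP subjects plus whatever spine subjects are evaluable by then; the third comes at about 80% of the total. Neither document says whether 0.001 is one- or two-sided.

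Once non-inferiority is shown, SAP 12.5.1.1 applies one criterion: "The superiority of BT524 is demonstrated if the 2-sided p-value is less than 0.05". Protocol 10.5 uses the same threshold. No level is given for superiority after an early stop.

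On size, SAP 6.2 states that "100 evaluable subjects per treatment arm are needed to demonstrate the non-inferiority of BT524 by using a t-test (equivalence) with 80% power", assuming SD 375 mL and a margin of 150 mL. It adds: "With 100 subjects per treatment arm superiority of BT524 can also be tested with a power of > 80"%, at two-sided 0.05 and effect size 0.5. Protocol 10.9 says the same.

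**The concern.** Testing non-inferiority and then superiority with the same confidence interval costs no alpha when there is one analysis. With several opportunities to stop, each at a different sample size, a superiority test at full 0.05 at the stopping look is a repeated test. The 0.001 boundary limits error for the non-inferiority hypothesis only. Because the 150 mL margin is large relative to the standard error, that boundary is easy to cross whenever the data favour BT524, so it gives the superiority hypothesis little protection.

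Superiority is a named objective in both documents, and the secondary analyses are declared exploratory. It is therefore the only other confirmatory claim the trial can make, and its error rate is the one that 12.5.2 vouches for. The same early stops also mean that superiority may be judged on far fewer than 100 per arm.

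**Working it through.** **Inputs.** SD 375 mL, margin 150 mL, 100 per arm, effect size 0.5, that is 0.5 × 375 = 187.5 mL (SAP 6.2). Interim alpha 0.001, interim 1 at about 50 subjects (25 per arm), interim 3 at about 160 (80 per arm) (SAP 10.0). 1:1 allocation (SAP 6.4). Assumed: interim 2 at 90-140 subjects in total (45-70 per arm), because the documents give only the PMP minimum; normal data; the same subjects in the PPS and FAS; no sample-size change.

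**The plan's own figures.**
- Non-inferiority: n = 2(1.96 + 0.8416)² × 375²/150² = 98.1, so 99 per arm. The exact noncentral t gives 100 per arm (power 80.4%). This agrees with the plan.
- Superiority at a fixed 100 per arm: 0.5 × √50 − 1.96 = 1.58, giving power 94%. This satisfies the stated figure.

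**Why the error rises.** In z units the margin is 150/(375√(2/n)) = 0.4√(n/2). The non-inferiority z equals the superiority z plus this amount. With two-sided 0.001 (critical value 3.29), the trial stops once the superiority z reaches:
- 25 per arm: 3.29 − 1.41 = 1.88
- 50 per arm: 3.29 − 2.00 = 1.29
- 80 per arm: 3.29 − 2.53 = 0.76

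All three lie below 1.96. Any look at which superiority would be significant at 0.05 therefore also stops the trial, and interim 1 alone spends about 2.5% one-sided. Later looks add to it.

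**Simulation.** The rule was: stop at an interim if estimate + 3.29 SE < 150 (3.09 if 0.001 is one-sided), or at the final analysis if estimate + 1.96 SE < 150; claim superiority if estimate + 1.96 SE < 0 at the stopping look. There were 2 million normal paths, with all three interims included.

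| Interim 2 (total) | Error, two-sided 0.001 | Power at 0.5 SD, two-sided 0.001 | Power, one-sided 0.001 |
|---|---|---|---|
| 90 | 4.7% | 75.1% | 66.1% |
| 100 | 4.5% | 75.4% | 67.1% |
| 120 | 4.3% | 78.2% | 71.0% |
| 140 | 4.3% | 82.6% | 75.4% |

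With one-sided 0.001 the error is 4.0-4.2%. Across all readings, including t-based tests and runs with interims 1 and 2 only, the error is 4.0-4.9% and power is 66-84%.

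**Where it comes from.** With the non-inferiority stop at interim 3 only, the error is 2.5%. Any z above 1.96 at 80 per arm stops there, and a path below 0.76 at that look almost never exceeds 1.96 at 100 per arm, so superiority is in effect tested once. Power is then about 89% (0.5 × √40 − 1.96 = 1.20).

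**Why power falls.** At effect size 0.5 the expected superiority z at interim 1 is 0.5 × √12.5 = 1.77. The chance of stopping there is P(Z > 1.88 − 1.77) = 46% (two-sided 0.001), and by interim 2 it is 84-98%. At interim 2 with 50 per arm, a path with z between 1.29 and 1.96 stops without superiority and loses the remaining subjects.

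**The case against.** **The 0.05 test after an interim stop is not written.** Protocol 10.5 describes superiority straight after the final analysis, 0.05 is assigned to the final analysis, and interims use the PPS while superiority uses the FAS (plus mFAS in the SAP). If superiority at an interim had to meet 0.001, its error would be at most about 2.0%. This stands in part: 4-5% belongs to one reading, though the natural one. But no text supplies another rule, and 12.5.2 asserts error control without one.

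**The interims may be over.** The SAP is dated 19 June 2023 and speaks of past interim analyses in the plural, without saying how many. If interims 1 and 2 passed without a stop and the arms are equal, the chance of a later false superiority claim is only about 0.15-0.55% (interim 2 at 100-120 subjects). This stands, and it limits the remedy to wording in that case.

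**The power statement is true.** A reader might infer that the figure of over 80% is false, or that the true value is 75-78%. The documents support neither. The statement is expressly for 100 per arm, where power is 94%. The narrower range needs interim 2 at about 90-120 subjects, two-sided 0.001 and a normal test; at 140 subjects power exceeds 80%.

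**Not every significant look must stop.** With a t-test at 25 per arm, a borderline superiority result gives a non-inferiority t of 2.01 + 1.41 = 3.42, below the critical 3.51. This is correct, but the t-based runs still give 4.1-4.9% error.

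**Interim 1 is planned with spine subjects only.** A reader might count this as part of the error problem. It is a separate question of generalisability.

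**Conclusion.** The statement in SAP 12.5.2 is wrong as written, because it overlooks the three interim stops. On the natural reading, the design-stage one-sided superiority error is about 4-5% against 2.5%, and the excess comes from interims 1 and 2. This assumes SD 375 mL, looks at 25, 45-70, 80 and 100 per arm, matching PPS and FAS, and no sample-size change; unblinded re-estimation was not modelled. The superiority power figure is correct for a fixed 100 per arm but is not the power of the design with early stopping, which is roughly 66-84%.

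A reader might infer that the trial's superiority claim has in fact been made at 4-5% error, or that the non-inferiority alpha is affected. Neither follows. The figures are properties of the design before any interim, they are not conditional on the trial having continued, and they concern the superiority test only.

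**What to change.** 1. **SAP 12.5.2:** replace the no-inflation statement with one that refers to the interim stops.
2. **SAP 12.5.1.1, with Protocol 10.5 to match:** state that superiority at two-sided 0.05 is tested once only, at the final analysis or at a stop at interim 3.
3. **SAP 10.0 and Protocol 10.8, for any interim 1 or 2 not yet performed,** choose one of two:
   - Remove option a), early termination for non-inferiority, at that look. With the stop left at interim 3 only, error is 2.5% and power about 89%. The cost, with equal arms and two-sided 0.001, is giving up about a 3% chance of stopping at interim 1 and 6-16% at interim 2.
   - Keep option a) and, in place of the single 0.05 test in item 2, set an adjusted superiority level at every look. About two-sided 0.03 restores roughly 2.5% error, but power must then be restated as about 60-70% (with 0.001 two-sided; lower if one-sided).

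   The first costs less power.
4. **SAP 6.2 and Protocol 10.9:** label the figure of over 80% as fixed-sample power at 100 per arm.
5. **SAP 10.0:** say which interims have taken place and whether 0.001 is one- or two-sided.

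If interims 1 and 2 have already passed without a stop, item 3 falls away and only the wording of 12.5.1.1, 12.5.2 and the power statement needs correcting. The cost is text in the SAP and protocol. SAP 3.0 finalises the plan before database lock, so the change can be made up to that point.

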12.5.3 Secondary Efficacy Parameters

All analyses of the secondary efficacy parameters will be performed on the FAS overall and for spinal surgery and abdominal surgery.

12.5.3.1 Correction of Fibrinogen Level

The proportion (%) of subjects with a successful correction of fibrinogen level (by FIBTEM A10) 15 minutes after start of first IMP administration will be compared between the treatment arms using a Cochran-Mantel-Haenszel (CMH) approach stratified by predictive blood loss (> 1,000 mL to \leq 2,000 mL and > 2,000 mL). The number and percentage of subjects with a successful correction of fibrinogen level 15 minutes after start of first IMP administration will be presented for both treatment arms with corresponding 95% confidence intervals. The estimated treatment effect (i.e., the difference in response rate between the treatment arms, BT524 – FFP/cryoprecipitate), corresponding 95% confidence interval, and 2-sided p-value for the difference will be presented.

The time to first successful correction of fibrinogen level (by FIBTEM A10) is assigned to the following categories: "Within 15 minutes after IMP start", "Greater than 15 and less than or equal to 90 minutes after IMP start", "Greater than 90 minutes after IMP start" and "Unsuccessful correction". The 4 categories will be compared between the two treatment arms using a Chi-square test.

In an additional analysis the time to first successful correction of fibrinogen level (by FIBTEM A10) is classified relative to the end of surgery into "Until end of surgery", "Not within surgery" or "Unsuccessful correction". The 3 categories will be compared between the two treatment arms using a Chi-square test.

For the above Chi-square tests, the number and percentage of subjects in each category will be presented for each treatment arm, together with an overall p-value for the difference between the two treatment arms.

The absolute values and change from baseline in fibrinogen levels by FIBTEM A10, together with the rate of fibrinogen restoring will be summarized with descriptive statistics over time by treatment arm. The absolute values at screening and change from screening at baseline will also be summarized for fibrinogen levels by FIBTEM A10.

In addition, the test results of MCF and Clauss assay will be summarized in the same way. The results of these three assays will be listed for the All Subjects Enrolled Set.

Mean with SD, median with interquartile ranges will be presented graphically over time for both treatment arms for FIBTEM A10, MCF and Clauss assay.

Pearson's Correlation will be tabulated between the FIBTEM A10 and Clauss assay for baseline and prior first dose values in the Fibrinogen FIBTEM A10 summary tables.

Analysis will be repeated for spinal and abdominal surgery.

12.5.3.2 Consumption of Transfusion Products after IMP until End of Surgery

The type of transfusion products includes autologous blood transfusion/cell salvage, allogenic platelet concentrates, allogeneic RBCs, allogeneic FFP, cryoprecipitate and other. Consumption of transfusion products is measured by the total amount of transfusion product (volume in mL and units [bags]) infused after start of first IMP and until the end of surgery.

This secondary efficacy endpoint will be descriptively summarized for volume (mL) and units (bags) of transfusion product for each product type by treatment arm. The number and percentage of subjects, using any transfusion product, together with the number and percentage of subjects using each transfusion product type will also be summarized by treatment arm.

Analysis will be repeated for spinal and abdominal surgery.

Two box-whisker plots will be created to present the amount of each type of transfusion product after start of first IMP until end of surgery by product type. One plot will show volume in mL and the other will show units (bags). Analysis will be repeated for spinal and abdominal surgery.

All the consumption of transfusion products in this study will be listed for the All Subjects Enrolled Set.

Summaries of subjects will also be provided for subjects with total avoidance of transfusion products post IMP administration. This will be repeated by surgery type.

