FFP is the liquid portion of blood that contains all the clotting factors, as well as other blood proteins and that is stored by freezing (WHO 2007). FFP is usually authorized nationally. Examples of FFP authorized in Germany are available from the website of the German authority Paul-Ehrlich-Institut (PEI). A solvent/detergent treated frozen plasma (PPD by PPD is nationally approved in several EU countries (PPD ).

Compared to fibrinogen concentrate FFP is stored frozen and must be thawed before use which is a limitation in time critical and potentially life-threatening situations such as severe bleeding. FFP contains 2.0 to 4.5 g/L of fibrinogen which is much lower than in fibrinogen concentrates (i.e. up to 10-fold lower than in BT524 with 20 g/L). Since FFP contains relatively low amounts of fibrinogen, it requires the administration of large volumes to provide meaningful increases in the fibrinogen plasma level. The large volumes carry the risk of hypervolemia, cardiac stress, circulatory overload, transfusion-related acute lung injury, hypothermia and metabolic complications once bleeding resolves (Bornikova et al., 2011; Elliott and Aledort, 2013; Mumford et al., 2014; Ofosu et al., 2008). Furthermore, the use of allogenic blood confers an additional risk for blood borne pathogens. Also noteworthy is the risk for transfusion related reactions, immune suppression, and a decrease in coagulation factors. There is also evidence that transfusion of allogenic blood is increasingly harmful as more blood is transfused (Verma et al., 2015).

As the concentration of fibrinogen in fibrinogen concentrates is markedly higher than in plasma the required dose to reach the fibrinogen target concentration can be administered in a minor volume. Furthermore, the amount of fibrinogen in FFP varies making it difficult to predict the increase in plasma fibrinogen concentration. The precisely defined fibrinogen content in fibrinogen concentrates allows accurate calculation of the amount of reconstituted concentrate needed for a targeted fibrinogen supplementation.

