# 6.6 Randomization Code

There will be a stratified randomization per surgery type. Subjects undergoing cytoreductive PMP surgery are to be randomized on a 1:1 basis to receive either BT524 or cryoprecipitate.

Randomization of PMP subjects to treatment will occur intra-operatively (pre-dose) when eligibility for the clinical study has been confirmed. Immediately after the prediction of clinically relevant bleeding > 2 L, requiring hemostatic treatment (high risk for the need of fibrinogen supplementation with BT524 or cryoprecipitate) during surgery, the person responsible for randomization will be informed and the randomization request will be sent. The person responsible for randomization retrieves the randomization code via Interactive Web Response System (IWRS) and informs the blood bank/pharmacy.

BT524 will be delivered to the operating room by the pharmacy. After randomization BT524 will be prepared in the operating room in accordance with the manufacturer's instructions and administered immediately after reconstitution by the unblinded anaesthesiologist.

After randomization, cryoprecipitate will be thawed and prepared for administration by the local blood bank, delivered to the operating room, and administered upon arrival.

In case the anaesthesiologist retrieves the randomization code via IWRS, the blood bank/ pharmacy will be informed accordingly and can provide the IMP.

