6.4 Randomization

There will be a stratified randomization per surgery type.

Subjects undergoing spine surgery are to be randomized on a 1:1 basis to receive either BT524 or FFP, and subjects undergoing cytoreductive PMP surgery are to be randomized separately on a 1:1 basis to receive either BT524 or cryoprecipitate.

For subjects undergoing spine surgery the randomization will be stratified according to the predictive blood loss: > 1,000 mL to \leq 2,000 mL and > 2,000 mL. The predictive blood loss will be recorded prior surgery.

Randomization of subjects to treatment will occur intra-operatively (predose) when eligibility for the clinical study has been confirmed.

For subjects undergoing spine surgery the following applies:

After an intra-operative blood loss of approximately 1 L, requiring hemostatic treatment (high risk for the need of fibrinogen supplementation with BT524 or FFP) during surgery, the randomization request will be sent to the pharmacy (if applicable). The pharmacy retrieves the randomization code via Interactive Web Response System (IWRS) and provides the prepared IMP to the unblinded anesthesiologist. In case the anesthesiologist retrieves the randomization code via IWRS, the pharmacy will be informed accordingly and can provide the IMP.

For subjects undergoing cytoreductive PMP surgery the following applies:

Randomization of PMP subjects to treatment will occur intra-operatively (pre-dose) when eligibility for the clinical study has been confirmed. Immediately after the prediction of clinically relevant bleeding > 2 L, requiring hemostatic treatment (high risk for the need of fibrinogen supplementation with BT524 or cryoprecipitate) during surgery, the person responsible for randomization will be informed and the randomization request will be sent. The person responsible for randomization retrieves the

randomization code via IWRS and informs the blood bank/pharmacy. BT524 will be delivered to the operating room by the pharmacy. After randomization, BT524 will be prepared in the operating room in accordance with the manufacturer's instructions and administered immediately after reconstitution by the unblinded anesthesiologist.

After randomization, cryoprecipitate will be thawed and prepared for administration by the local blood bank, delivered to the operating room, and administered upon arrival.

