7.0 Study Parameters and Covariates

7.1 Primary Efficacy Parameter

The primary efficacy parameter is determined from the intra-operative blood loss after the decision to treat the subject with IMP until the end of the surgery as measured by the amount of blood from the blood suction unit and the amount of blood from swabs, surgical cloths and compresses. The end of surgery is defined as time of last suture.

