8.21 Time to Start of First Investigational Medicinal Product Infusion

Time to start of first IMP infusion = Start time of first IMP administration - Time of decision to treat subject with IMP.

8.22 Total planned Investigational Medicinal Product Volume Total planned IMP volume = Sum of all planned IMP volume.

8.23 Total actual Investigational Medicinal Product Administered Total actual IMP administered = Sum of all actual IMP administered.

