12.5.3.3 Amount of RBCs infused after IMP until End of Surgery

The amount (volume in mL and units [bags]) of RBCs (allogeneic and autologous) infused after start of first IMP administration until the end of surgery will be summarized by treatment arm.

An ANOVA analysis will be performed with the amount of RBCs required as the dependent variable and the predictive blood loss (> 1,000 mL to \leq 2,000 mL and > 2,000 mL) as a covariate. The least square means and difference in least square means will be presented with the corresponding 95% confidence intervals and 2-sided p-value. This will be repeated by surgery type.

In addition, a subgroup analysis of the amount of RBCs will be performed for the FAS. Subgroups are predictive blood loss as well as spinal and abdominal surgery. The amount of RBCs will be analyzed using an ANOVA for each subgroup. The least square means and difference of least square means together with 95% confidence intervals and p-values for each subgroup will be presented.

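### RBC use is counted from first IMP, which is expected later in the thawed-comparator arm, so control RBC use is likely understated relative to BT524 by an amount the documents cannot fix

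*SAP*

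**What the plan says.** SAP 12.5.3.2 measures transfusion products "infused after start of first IMP and until the end of surgery". SAP 12.5.3.3 takes RBCs, allogeneic and autologous, "infused after start of first IMP administration until the end of surgery will be summarized by treatment arm", and then fits an ANOVA with predictive blood loss, giving a confidence interval and a two-sided p-value, repeated by surgery type. Protocol 9.1.3.2 and SAP 7.2.1 define both endpoints with the same starting point.

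The primary endpoint starts elsewhere. SAP 7.1 takes "intra-operative blood loss after the decision to treat the subject with IMP until the end of the surgery". Protocol 7.1 has the decision time recorded, and in Protocol section 3 the decision comes before randomization.

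The arms reach first IMP by different routes. At the PMP site, SAP 6.4 has BT524 prepared in the operating room and "administered immediately after reconstitution by the unblinded anesthesiologist". For the comparator it says: "After randomization, cryoprecipitate will be thawed and prepared for administration by the local blood bank, delivered to the operating room, and administered upon arrival". Protocol 6.6 agrees. For FFP, the Protocol introduction says that "FFP is stored frozen and must be thawed before use".

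Protocol 6.10 bars platelets, FFP, cryoprecipitate and hemostatic agents before and during the first IMP dose, but allows RBCs. SAP 8.21 derives the delay: "Time to start of first IMP infusion = Start time of first IMP administration - Time of decision to treat subject with IMP". SAP 12.3.1 summarizes it by treatment, and SAP 12.3.4 summarizes RBCs given before first IMP in the SAF.

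**The concern.** Randomization makes the arms comparable from the moment of allocation. A window that opens later, at an event whose timing depends on the allocated product, loses that protection. RBCs given while the comparator is being thawed and delivered fall outside the endpoint. In the BT524 arm the corresponding gap is expected to be shorter, so less is left out.

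The plan is also inconsistent with itself. Blood lost during the thaw counts toward the primary endpoint, but RBCs given during the thaw to replace that blood do not count toward the RBC endpoint.

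At stake is a treatment comparison reported with an interval and a p-value. Protocol 8.1 presents timely hemostatic intervention as part of the main benefit of BT524, yet a window that opens at first dose cannot register RBCs avoided because treatment began sooner. The likely distortion is against BT524.

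**Working it through.** **The plan's own figure.** The only sample size given is for the primary endpoint (SAP 6.2): SD 375 mL, margin 150 mL, one-sided alpha 2.5%, 80% power, 100 evaluable per arm. The normal approximation gives n = 2 × (1.960 + 0.842)² × (375/150)² ≈ 98.1, so 99 per arm. The noncentral t gives 80.4% power at 100 per arm, so the figure reproduces. This point does not touch it, because the primary window already opens at the decision to treat. No figure is given for the RBC or transfusion endpoints.

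**What can fall in the gap.** Under Protocol 6.10, hemostatic products should not appear before first IMP. That leaves RBCs and possibly cell salvage.

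**What the planned summaries show.** SAP 12.3.1 will show the delay by treatment. SAP 12.3.4 will show RBCs before first IMP, but does not separate those given before the decision from those given after it. No planned RBC or transfusion analysis starts at the decision or at randomization, and none adjusts for the delay.

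**Illustration.** Let W be the minutes from decision to last suture, and d_B and d_C the delays from decision to first IMP in the BT524 and control arms. Assume a constant RBC rate over W and equal true use in both arms.

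- Share of post-decision use counted in an arm = 1 − d/W
- Excess window lost in control relative to BT524 = (d_C − d_B)/W
- Ratio of counted use, control to BT524 = (1 − d_C/W)/(1 − d_B/W)

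All values of W, d_B and d_C below are assumptions; the documents give none.

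Excess window lost:

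- extra delay 15 min, W = 360 min: 15/360 = 4%
- extra delay 30 min, W = 240 min: 30/240 = 12.5%
- extra delay 45 min, W = 120 min: 45/120 = 37.5%, or 38%

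Ratio of counted RBCs, control to BT524, with d_B = 10 min:

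| d_C (min) | W = 120 | W = 240 | W = 360 |
|---|---|---|---|
| 10 | 1.00 | 1.00 | 1.00 |
| 20 | 0.91 | 0.96 | 0.97 |
| 30 | 0.82 | 0.91 | 0.94 |
| 45 | 0.68 | 0.85 | 0.90 |
| 60 | 0.55 | 0.78 | 0.86 |

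Per unit of true RBC use, the false difference for unequal delays runs from (20 − 10)/360 = 0.03 units to (60 − 10)/120 = 0.42 units. It is zero when delays are equal, and also when no RBCs are given in the gap.

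**After the change.** If both arms count from the decision to treat, the counted share is 1 in each and this artefact is zero by construction.

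**The case against.** The strongest objection is that neither direction nor size is shown. There are no decision-to-dose times and no RBC timings in the documents. Protocol section 3 ties intra-operative transfusion to hemoglobin, the amount and speed of loss, and clinical condition, so blood lost during the thaw may be replaced after first IMP and then be counted. PMP dosing is pre-emptive, which makes a constant RBC rate from the decision doubtful. All of this stands, and it is why the direction is called likely and the figures illustrative.

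Three stronger readings are tempting, and the documents do not support them:

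- *The whole transfusion endpoint understates control use.* Protocol 6.10 keeps hemostatic products out of the gap. SAP 12.5.3.2 also lists FFP and cryoprecipitate without saying whether randomized comparator doses are left out. If they are counted, total control use is overstated, the opposite direction.
- *The delay is established for every control subject.* Thawing after randomization is documented for the single PMP site. For spine surgery, SAP 6.4 has the pharmacy supply prepared IMP after retrieving the code but does not time the thaw, and the spinal protocol text is not available.
- *4% to 38% is the share of control RBC use left uncounted.* It is the excess over BT524. The control arm's total uncounted share is d_C/W, which includes the delay common to both arms. The 38% also pairs the longest assumed delay with the shortest assumed surgery.

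It is also fair to say that counting from first IMP is a consistent, deliberate definition of use after treatment starts, and that the planned summaries make the problem visible. They do not correct it. SAP 10.0 refers to past interim analyses and says that interim analyses use unblinded data, so replacing a protocol-defined endpoint now would be hard to defend. That argues for adding an analysis and keeping the existing one.

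**Conclusion.** The concern holds for the RBC endpoint, and for the RBC and possibly cell-salvage components of the transfusion endpoint. Their window opens at a post-randomization event that is expected later in the comparator arm: documented for cryoprecipitate in PMP surgery, inferred for FFP in spine surgery. Control RBC use is likely understated relative to BT524.

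The size cannot be computed from the documents. The 4% to 38% excess loss of window rests on an assumed extra delay of 15 to 45 minutes and 2 to 6 hours of remaining surgery. Reading it as a loss of RBC use also needs a constant RBC rate. A reader might infer a proven bias against BT524; the documents support only a conditional one, which vanishes with equal delays or no RBCs in the gap.

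The consequence is limited. SAP 12.5.2 treats secondary analyses as exploratory, the likely direction would not manufacture an RBC benefit for BT524, and the primary endpoint is not affected. The change is still worth making, because the RBC comparison is tested and the remedy is cheap.

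**What to change.** Before database lock:

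1. Add to SAP 12.5.3.3 a prespecified FAS analysis of RBCs from the recorded decision time until last suture, with the same ANOVA model, shown beside the from-first-IMP analysis. Do the same descriptively for RBCs and cell salvage in SAP 12.5.3.2. List the addition in SAP 4.1.
2. State in SAP 12.5.3.2 whether randomized FFP and cryoprecipitate doses are excluded from the transfusion total.
3. Check SAP 8.5.1 against the new window. A transfusion on the day of first IMP with no start time is set to the first-IMP time, so it would be counted even if it was given before the decision. If only the hour is known and it differs from the hour of first IMP, minutes are set to 00, which could move a transfusion given after the decision to before it.

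The cost is one extra derivation and table plus a few lines of SAP text. Decision time is already recorded, and the SAP already handles transfusion start times. The protocol-defined endpoint and the sample size stay as they are. The downside is a second RBC result that may differ from the first; the by-arm delay from SAP 8.21 should be shown with both.
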